#### 4.5.5 Electrocardiogram

#### 4.5.5.1 **Definitions and Derivations**

Part A ECG evaluation includes:

- RR interval (msec)
- PR interval (msec)
- QRS duration (msec)
- QT interval (msec)

- Heart rate (beats/min)
- QTcF interval (msec)
- Overall evaluation (normal, abnormal, borderline). If abnormal, reason and clinical significance are also collected.

ECGs will be performed in triplicate and the average of replicate measurements will be analyzed. Change from baseline is defined as the post-baseline visit value minus the baseline value.

Potentially clinically significant criteria for ECG parameters are as follows:

- QRS duration > 118 ms
- PR interval > 210 ms
- RR < 600 ms (resting heart rate > 100 bpm)
- RR > 1330 ms (resting heart rate < 45 bpm)

OTcF intervals are classified as:

- > 450 msec
- > 480 msec
- > 500 msec

QTcF increases compared to baseline are classified as:

- > 30 msec
- $\geq$  60 msec

### 4.5.5.2 Presentations

ECG tables and listings will be based on the on-treatment data only in the safety population and presented for each treatment group. ECG parameters (except for the overall evaluation) will be summarized with n, mean, median, SD, minimum, and maximum, at each visit and for change from baseline.

Number and percentage of participants within each QTcF interval classes at any time during the on-treatment period will be also reported together with number and percentage of participants within QTcF increase classes at any time during the on-treatment period.

ECG parameters fulfilling potentially clinically significant criteria at any time during treatment will be summarized by treatment.

Overall evaluation will be analyzed as shift from baseline to last value in the on-treatment period.

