#### Assessments cover:

- Observed value
- Absolute change from baseline values over time
- ECG parameters fulfilling potentially clinically significant criteria at any time during treatment, including QRS duration > 118 ms, PR interval > 210 ms, RR < 600 ms (resting heart rate > 100 bpm), and RR > 1330 ms (resting heart rate < 45 bpm)
- QTcF exceeding 450, 480, and 500 ms at any time during treatment
- Change in QTcF at any time during treatment as compared to baseline exceeding 30 ms and 60 ms

For details of the safety analysis, refer to Section 4.5.

A second primary objective is 'to assess the immunogenicity of cotadutide' with associated endpoint "incidence of ADAs to cotadutide and titer during treatment and follow-up." Details of analysis of anti-drug antibodies (ADAs) can be found in Section 4.4.

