# 4.5.3.2 Presentations

Tables, graphs, and listings for laboratory data will be based on the on-study data only in the safety population and presented for each treatment group.

Laboratory test results for continuous clinical laboratory parameters will be summarized with n, mean, SD, median, minimum and maximum by treatment and analysis visit, and for change from baseline. Categorical parameters will be summarized by number and percentage of participants in each category by treatment and analysis visit. A frequency table will present number of participants reporting at least 1 treatment-emergent abnormality in chemistry, hematology, or coagulation clinical safety laboratory tests by highest category (Level 1 to 3, where Level 3 is the most extreme; refer to Appendix A for ranges). Low and high abnormalities for the same laboratory parameter will be summarized separately. Shifts from baseline to maximum value during the on-study period will be presented for urinalysis qualitative parameters.

Potential Hy's Law cases will be summarized by treatment and listed, and will be displayed for both the on-treatment and on-study periods. Maximum on-treatment ALT, AST, and TBL will be analyzed using categories described below and using baseline as defined in this document.

Participants with normal/near normal ALT ( $\leq 1.5 \times \text{ULN}$ ) at baseline:

- ALT < 3 × ULN and bilirubin not elevated (Non-Gilbert: Not elevated = total bilirubin < 2 × ULN. Gilbert: Not Elevated = direct bilirubin < 2 × baseline and INR  $\leq$  1.5)
- ALT <  $3 \times$  ULN and bilirubin elevated (Non-Gilbert: Elevated = total bilirubin  $\geq 2 \times$  ULN. Gilbert: Elevated = direct bilirubin  $\geq 2 \times$  baseline or INR > 1.5)
- ALT  $> 3 \times ULN$  and bilirubin not elevated
- ALT  $\geq$  3 × ULN and bilirubin elevated
- ALT  $> 5 \times ULN$  and bilirubin not elevated
- ALT  $\geq$  5 × ULN and bilirubin elevated
- ALT  $> 8 \times ULN$  and bilirubin not elevated
- ALT > 8 × ULN and bilirubin elevated
- (repeat same categories with AST instead of ALT)

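### The ECG overall evaluation is tabulated only at the last on-treatment reading, so a transient abnormality that crosses no interval threshold enters no ECG summary table

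*SAP*

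**What the plan says.** SAP Section 4.5.5.1 defines the variable: "Overall evaluation (normal, abnormal, borderline). If abnormal, reason and clinical significance are also collected". Section 4.5.5.2 then gives it one analysis: "Overall evaluation will be analyzed as shift from baseline to last value in the on-treatment period". The same section excludes it from the visit-by-visit tables: "ECG parameters (except for the overall evaluation) will be summarized with n, mean, median, SD, minimum, and maximum, at each visit".

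The measured intervals are treated differently. Section 4.5.5.2 states that "ECG parameters fulfilling potentially clinically significant criteria at any time during treatment will be summarized by treatment", and the criteria listed in Section 4.5.5.1 are QRS, PR and RR limits. QTcF has its own any-time table: "Number and percentage of participants within each QTcF interval classes at any time during the on-treatment period", together with classes of QTcF increase. The treatment-emergent rule in Section 4.5 is worded for ECG intervals and does not extend to the overall evaluation.

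For another categorical safety variable the SAP takes the worst value: "Shifts from baseline to maximum value during the on-study period will be presented for urinalysis qualitative parameters" (Section 4.5.3.2). Laboratory and vital-sign abnormalities are counted when they occur at least once (Sections 4.5.3.2 and 4.5.4.2).

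**The concern.** The overall evaluation is the ECG variable able to carry findings that the interval measurements do not describe, such as rhythm, conduction morphology or ST-T change. Protocol Section 8.2.4 arranges a blinded central cardiologist's reading of morphology, and the SAP records the reason and clinical significance of each abnormal result. A last-value shift describes status at the end of treatment. It does not show how many participants had an abnormal reading at some point while on drug.

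That question matters here. Safety is the primary objective, protocol Section 4.2.3.1 gives cardiovascular safety particular attention, and all scheduled uptitration steps fall at Weeks 4 to 24, before a completer's last reading. What is at stake is a between-arm comparison of transient ECG abnormalities, which no planned ECG summary table provides for this variable.

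**Working it through.** There is no sample-size or power figure to reproduce. The check is a count of visits, a trace through the tables and a simple illustration.

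**1. Visits.** The protocol's schedule of activities (Table 4) and SAP Table 3 place post-baseline ECGs during treatment at Weeks 4, 8, 12, 16, 20, 24, 32, 40 and 48, which is 9 visits. SAP Section 3.3.1.2 ends the on-treatment window for ECG 7 days after treatment discontinuation, so the follow-up ECG 4 weeks later normally falls outside it. For a completer the last on-treatment value is therefore Week 48, and 9 − 1 = 8 earlier overall evaluations do not enter the shift table. Early discontinuers have fewer than 8.

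**2. Trace.** Take a normal baseline, an abnormal morphology reading at Week 16 with QRS, PR, RR and QTcF all inside their limits, and a normal Week 48.

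| Planned ECG output | Is the Week 16 overall category counted? |
|---|---|
| By-visit summaries | No, the overall evaluation is excluded |
| QRS, PR, RR criteria at any time | No threshold crossed |
| QTcF level and increase at any time | No threshold crossed |
| Shift of overall evaluation | Tabulated as normal-to-normal |
| Listing | Yes, as an individual record |

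The rule in SAP Section 3.3.2 that prefers the worse category does not change this. It chooses among records on one selected day and does not carry a worst value across visits.

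**3. Illustration of size.** The documents give no rate of abnormal overall evaluations, so the per-visit probability p is an assumption. So are a normal baseline and all 9 visits being attended. The planned table shows a proportion p, from the last visit. The proportion ever abnormal depends on persistence:

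- full persistence within a participant: p
- independent visits: 1 − (1 − p)^9

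| Assumed p | Tabulated (last value) | Ever abnormal, full persistence | Ever abnormal, independent visits | Difference, independent visits |
|---|---|---|---|---|
| 3% | 3% | 3% | 1 − 0.97^9 = 24.0% | 24.0 − 3 = 21.0 points |
| 5% | 5% | 5% | 1 − 0.95^9 = 37.0% | 37.0 − 5 = 32.0 points |

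With about 55 randomized 2:1:2:1, each cotadutide dose has about 55 × 2/6 = 18.3 participants. At p = 3% under independence, about 0.240 × 18.3 = 4.4 per dose would have at least one abnormal reading, and about 0.03 × 18.3 = 0.5 would be abnormal at the last visit. Under full persistence both figures are 0.5.

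**The case against.** The strongest reply is that little of clinical importance would be lost, and most of it stands.

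- **Adverse events.** A reader might infer that transient rhythm or morphology findings vanish from the safety report. The documents do not support that. The investigator judges each ECG for clinical significance (protocol Section 8.2.4). Cardiovascular events and increased heart rate are events of special interest, and SAP Section 4.5.2.2 tabulates all on-study AEs whatever the last ECG shows. The limit of this backstop is that it depends on the investigator's reporting: protocol Section 8.3.5 sets explicit rules for laboratory values, vital signs and physical examination but does not mention ECG.
- **Intervals.** A reader might infer that ECG as a whole is handled less carefully than laboratory data. It is not. The interval criteria are counted at any time, so a rhythm or conduction disturbance that crosses a limit is captured. Only the overall evaluation differs.
- **Unused data.** It would also be wrong to say that 8 of 9 ECGs go unused. Their intervals feed the by-visit and any-time tables. Only their overall category is untabulated.
- **Endpoint status.** The ECG assessments under the protocol's primary objective (Section 3.1) do not include the overall evaluation, so the SAP contradicts nothing and no named primary assessment is weakened.
- **Listings.** All scheduled and unscheduled assessments are listed (SAP Section 3.3.3), and with about 18 participants per dose a listing can be read person by person. It still gives no tabulated comparison between arms.
- **Choice of summary.** Last value answers a legitimate question, and a worst-value shift picks up chance findings in every arm. That supports keeping the last-value table. It is not a reason to leave out the other.

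**Conclusion.** The point holds in a limited form. Under SAP Section 4.5.5.2, an abnormal overall evaluation that crosses no interval threshold and clears before the last on-treatment ECG is in no ECG summary table. It is shown as normal-to-normal when the baseline and last readings are normal. For a completer this applies to eight of nine scheduled post-baseline treatment visits. The handling is out of line with the SAP's own treatment of qualitative urinalysis and of laboratory and vital-sign abnormalities.

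The structural gap follows from the text and depends on no assumed rate. The size does. The 24% and 37% are upper ends of illustrations that need independent visits and rates the documents do not supply, and the difference falls to zero if abnormalities fully persist. They should not be read as an expected loss. With AE tables, listings and any-time interval counts in place, this is a cheap improvement of minor severity.

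**What to change.** In SAP Section 4.5.5.2, add a shift from baseline to the worst on-treatment overall evaluation and keep the last-value shift beside it. Use the categories already collected (normal, borderline, abnormal) and split abnormal by the recorded clinical significance. State the severity order used, because the SAP ranks abnormal above normal but does not place borderline.

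The cost is one further column or panel in an existing table, with no new data collection. The downside is more chance findings in every arm, since nine readings give more opportunities than one. The placebo column shows that background rate.

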# 5 TIMING OF ANALYSIS

Analysis will be conducted by the sponsor after final clinical data lock.

# Appendix A Reference Ranges

**Table A1** Reference Table for Abnormality Level Criteria Cutoffs, Chemistry

Parameter	Units	Low/High	Level 1	Level 2	Level 3
Sodium	mEq/L	Low	< 132	< 130	< 125
		High	> 150	> 155	> 160
Potassium	mEq/L	Low	< 3.6	< 3.4	< 3.0
		High	> 5.5	> 6.0	> 6.5
Chloride	mEq/L	Low	< 95	< 88	< 80
		High	> 108	> 112	> 115
Bicarbonate	mEq/L	Low	< 20	< 18	< 15
		High	N/A	N/A	>30
Blood urea nitrogen	mg/dL	High	> 23	> 27	> 31
Glucose, Fasting	mg/dL	Low	< 70	< 54	N/A
		High	≥ 100	≥ 126	N/A
Glucose, Random	mg/dL	Low	< 70	< 54	N/A
		High	N/A	≥ 200	N/A
Calcium	mg/dL	Low	< 8.4	< 8.0	< 7.5
		High	> 10.5	> 11.0	> 12.0
Phosphorous	mg/dL	Low	< 2.5	< 2.0	< 1.4
Albumin	g/dL	Low	< 3.1	< 2.5	< 2.0
Amylase	U/L	High	> 1.1 × ULN	> 1.5 × ULN	> 3.0 × ULN
Lipase	U/L	High	> 1.1 × ULN	> 1.5 × ULN	> 3.0 × ULN
Creatinine	mg/dL	Increase	≥1.5 × baseline	≥2.0 × baseline	≥3.0 × baseline
eGFR	mL/min/1.73m 	Decrease	≥ 25% decrease from baseline	≥ 50% decrease from baseline	≥ 75% decrease from baseline
Alkaline Phosphatase	U/L	High	> 1.5 × ULN	> 2.0 × ULN	> 3.0 × ULN

eGFR, estimated glomerular filtration rate; N/A, not applicable; ULN, upper limit of normal.

A laboratory result will be considered Level 1 only if outside of the normal laboratory reference range.

Table A2 Reference Table for Abnormality Level Criteria Cutoffs, Hematology, and Coagulation

	Ť.	1			
Parameter	Units	Low/High or Decrease/Incre ase	Level 1	Level 2	Level 3
WBC	10  /L	Low	< 3.500	< 3.000	< 1.000
		High	> 10.800	> 13.000	> 15.000
Hemoglobin	g/dL	Decrease	N/A	decrease from baseline of > 1.5	decrease from baseline of > 2.0
		Increase	N/A	increase from baseline of > 2.0	increase from baseline of > 3.0
Hemoglobin (male)	g/dL	Low	≤ 13.5	< 12.5	< 10.5
Hemoglobin (female)	g/dL	Low	≤ 12.0	< 11.0	< 9.5
Platelets	10  /L	Low	< 140	< 125	< 100
Lymphocytes	10  /L	Low	< 1.000	< 0.750	< 0.500
		High	> 4.000	> 10.000	> 20.000
Neutrophils	10  /L	Low	< 2.000	< 1.000	< 0.500
Eosinophils	10  /L	High	> 0.650	> 1.500	> 5.000
Prothrombin Time	seconds	High	> 1.1 × ULN	> 1.3 × ULN	> 1.5 × ULN
Activated partial thromboplastin time	seconds	High	> 1.0 × ULN	> 1.21 × ULN	> 1.41 × ULN

N/A, not applicable; ULN, upper limit of normal; WBC, white blood cell.

